Exclusion criteria: Age < 18 years, age > 65 years, complication of CRS (f.e. mucocele, invasive fungal rhinosinusitis), other diagnosis than CRSwNP (inverted papilloma, antrochoanal polyp etc), previous external sinus surgery or Draf 3 procedure (or indication for external approaches or Draf 3, bleeding diathesis, pregnancy/ breastfeeding, cystic fibrosis, primary ciliary dyskinesia (PCD), sarcoidosis, granulomatosis with polyangiitis (GPA), eosinophilic granulomatosis with polyangiitis (EGPA), immunosuppression (diagnosed Specific Antibody Deficiency (SAD), CVI, HIV or use of biologicals/immunosuppressive medication), immunotherapy, daily use of systemic corticosteroids, communication problems (f.e. neurological/psychiatric disease, language skills), unlikely to comply, other severe disease, inability to be operated.

Randomization and surgery. The randomisation is performed by a professional statistician in blocks and for each center. The randomisation group of consecutive patients is sealed in numbered envelopes and kept in a locked room; the envelope is opened during the visit after informed consent. The patients are randomized for 1. total ethmoidectomy +sphenotomy +frontal opening (Draf2a) and 2. removal of polyps with uncinectomy, +/-opening of the natural ostium +/- ground lamella but not opening sphenoid or frontal sinus unless already opened in a previous surgery (Figure 1). Sinus operations are performed under general or local anesthesia on both sides with standard techniques and instrumentation by ENT specialists. Videoendoscopy is recorded at completion of extended surgery. Extended sinus surgery is usually performed with navigation. If not contraindicated, the patients may receive peroral corticosteroids 10-14 days perioperatively starting a few days before surgery.

Follow-ups. Patients are monitored before and during the follow-ups. The follow-ups are 3, 6, 9, 12,18 and 24 months postoperatively. During each visit the validated questionnaires and nasal endoscopy are performed. Nasal patency and olfaction as well as spirometry and PEF are monitored. Blood and tissue samples and low-dose sinus CT scans (1 year postop) are performed (Figure 1).

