We also monitor intra-operative factors (such as anesthesia method, use of local e.g. cocaine, terracortril and systemic medication, e.g. antibiotics and dexametasone, operation time and bleeding, use of tampons, complications, mucopurulent excretions, early postoperative factors such as duration of hospitalization, timing of tampon removal, duration of sick leave, medication, complications, visits and hospitalizations; as well as exacerbations, need of medication (po. corticosteroids; antibiotics). Time of surgery and equipment needed is recorded.

The primary end point is the change in SNOT-22 1 and 2 years postoperatively. Secondary end points include changes in polyp score, LM CT score, hrQOL, loss of productivity, nasal patency (peak nasal inspiratory flow (PNIF) +/- acoustic rhinometry (ARM), olfaction test (Sniffin' Sticks, identification), lung function (spirometry and PEF) and pathologic findings. Safety (complications, adverse effects) costs and loss of productivity between study arms will be compared. The study will compare costs of CRSwNP and asthma treatment one year before and two years after surgery. In addition to data from medical records and patients, data may be collected from national health records.

During and after follow-up, patients can undergo revision operation or other treatment, if needed and patients will still be followed for the duration of the study. Patient's disease control is monitored postoperatively by ENT-doctor as described earlier. Patients who have uncontrolled disease not responding to medication undergo CT scans and are evaluated for the need of removal of polyps and re-ethmoidectomy according to their study arm. In addition, AERD-patients are evaluated for their willingness in ASA desensitization and to participate in the AirGOs clinical trial.

B. Genome-scale search for biological key-factors

Peripheral blood, intranasal mucus and cell brushing samples, nasal polyp and/or nasal mucosal biopsies are taken from clinical trial participants and volunteer control subjects. The samples will be stored at Helsinki Biobank. These samples are collected in a time-series manner (pre-intervention, 24w post start of intervention) and biopsies are taken under local anesthesia. Nasal brushings and mucus swabs are collected from nasal mucosa, under middle turbinate, without local anesthesia. If possible, subjects are asked to be for 7-14 days without CRS medication before taking nasal specimens.

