Statistics. Data analysis will be carried out on the relationship between two operative treatments, and between ASA- and placebo desensitization. Variables tested in the statistical models include age, gender, exposures, infections, diseases, symptoms, exacerbation-rate, satisfaction, image-findings, endoscopic findings, operation, perioperative factors (such as operation time), complications, sick leave, biological factors (predisposing SNPs, alterations in transcriptome or microbiome), occupation, asthma, grade of nasal polyps, AERD, allergy, revision-rate, side-effects of AD, hospitalizations, sick leaves, and other factors at different time-points. We will use several software: R 3.0.2, SPSS 22.0 Statistical Software Package (SPSS, Chicago, IL) and STATA (Release 13.1 software, StataCorp, Texas, USA). For comparisons, the results will be analyzed by Logistic regression, Student's t-, Chi-square, (nonparametric) Fisher's exact and Mann Whitney U test, Cox's proportional-hazards model, cumulative hazard function H(t), hazard ratio, Kaplan–Meier method, and log rank test. Genetic calculations on Hardy–Weinberg equilibrium and linkage disequilibrium will be performed with Arlequin (version 3.5) using SPSS Statistics (version 20.0, IBM). P-values less than 0.05 are considered statistically significant. Results of logistic regression are reported as odds ratios (OR) with 95% confidence intervals. All models will be adjusted by selected covariates (potential confounding factors).

4. Implementation of the study plan

The **operative** trial will be performed during the years 1-5, starting in September 2018. The wetlab will be performed during the years 2-6. The statistical analyses, data management, search for literature, and manuscript(s) will be performed during the years 1-6.

5. The study group and collaborators

The study group:

Docent, Otorhinolaryngologist (HUH) [name] is director and is responsible for the management of the project and conducts the AirGOs Operative study in ENT hospital of HUH.

Docent, Pulmonologist (HUH) [name], is vice-director and conducts pulmonological assessment in Skin and Allergy Hospital (HUH/IAS).

MD, PhD, Otorhinolaryngologist (HUH) [name], is vice director and performs operative and clinical study in ENT Hospital

Docent [name] (HUH) performs in IAS and conducts data management, manuscripts and sample studies

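### No analysis model is named for the primary SNOT-22 change; the listed tests that fit it are unadjusted, and neither baseline SNOT-22 nor centre is named as a covariate

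*Combined protocol and SAP*

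**What the plan says.** The end-point paragraph of section 3A (Operative study) states: "The primary end point is the change in SNOT-22 1 and 2 years postoperatively".

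The Statistics section gives one general list of methods for the whole project: "For comparisons, the results will be analyzed by Logistic regression, Student's t-, Chi-square, (nonparametric) Fisher's exact and Mann Whitney U test", then Cox regression, Kaplan-Meier and the log-rank test. No method is assigned to the primary end point. On adjustment it says "All models will be adjusted by selected covariates (potential confounding factors").

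The same section also lists the variables that will enter models: "Variables tested in the statistical models include age, gender, exposures, infections, diseases, symptoms, exacerbation-rate, satisfaction", and further on "perioperative factors (such as operation time), complications, sick leave", ending with "sick leaves, and other factors at different time-points". Neither baseline SNOT-22 nor centre is named.

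Both are available. SNOT-22 is collected before surgery and is an entry criterion (at least 30). On allocation, the Randomization and surgery paragraph says: "The randomisation is performed by a professional statistician in blocks and for each center". Visits are at 3, 6, 9, 12, 18 and 24 months, and patients who have a revision stay in follow-up: "patients will still be followed for the duration of the study".

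**The concern.** A score measured before and after treatment can be compared between arms on the follow-up value, on the change, or on the follow-up value adjusted for baseline. These three analyses have different precision, and the plan does not say which will be used. A t-test on change subtracts the whole baseline score. Baseline adjustment (ANCOVA) estimates how much of it to subtract, so its residual SD cannot be larger, at the cost of one degree of freedom. It also removes chance baseline imbalance between arms.

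The adjustment sentence does not settle the matter, because no linear model is listed for it to act on and the covariates are left open. The variable list cannot stand in for a covariate set in the arm comparison: operation time, complications and sick leave become known only after randomisation and may be consequences of the operation itself.

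Two things are at stake. One is power that the collected data could supply. The other is that an open choice of analysis, made after the data are seen, raises the type I error.

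**Working it through.** **Inputs from the protocol (Power calculation):** difference 9, SD 20, alpha 0.05, power 0.8, 79 per arm. The text does not say whether 20 is the SD of the postoperative score or of the change. Sidedness is not stated; two-sided fits the stated n (one-sided would need 62 per arm).

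**Assumed, because the documents do not give them:** baseline-to-follow-up correlation r from 0.2 to 0.7; baseline SD either equal to the follow-up SD or 15 (the entry threshold narrows the baseline range); share of variance due to centre; between-visit correlation.

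**Step 1. The plan's figure.** Standard error = 20·√(2/79) = 3.18, noncentrality = 9/3.18 = 2.83, df 156. Noncentral t power = 0.803. The planned size therefore matches an unadjusted two-sample t-test.

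**Step 2. SD 20 is the postoperative SD.** With baseline SD s_b:
- SD of change = √(s_b² + 400 − 40·r·s_b)
- ANCOVA residual SD = 20·√(1 − r²), df 155

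Example at r = 0.2, s_b = 20: change SD = √(400 + 400 − 160) = 25.3, power 0.603; ANCOVA SD = 20·√0.96 = 19.6, power 0.818.

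| r | t-test on change, s_b = 20 | t-test on change, s_b = 15 | ANCOVA |
|---|---|---|---|
| 0.2 | 0.603 | 0.706 | 0.818 |
| 0.3 | 0.661 | 0.760 | 0.838 |
| 0.4 | 0.728 | 0.817 | 0.866 |
| 0.5 | 0.803 | 0.877 | 0.901 |
| 0.6 | 0.882 | 0.932 | 0.940 |
| 0.7 | 0.952 | 0.975 | 0.976 |

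The gain runs from 0.215 down to 0.023 with equal SDs, and from 0.112 down to 0.001 with baseline SD 15.

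**Step 3. SD 20 is the SD of change.** The t-test on change has power 0.803 throughout. Solving for the follow-up SD that makes the change SD 20 gives:

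| r | ANCOVA, equal SDs | ANCOVA, baseline SD 15 |
|---|---|---|
| 0.2 | 0.952 | 0.934 |
| 0.3 | 0.937 | 0.891 |
| 0.4 | 0.919 | 0.848 |
| 0.5 | 0.901 | 0.816 |
| 0.6 | 0.881 | 0.803 |
| 0.7 | 0.862 | 0.820 |

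The largest gains are about 0.150 and 0.131; the smallest is zero.

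**Step 4. Centre.** Because allocation is blocked within centre, the unadjusted test has true variance 400·(1 − share) but estimates 400. The adjusted analysis uses SD 20·√(1 − share), df 151.

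| Share of variance | Unadjusted power | Adjusted power | Unadjusted type I error |
|---|---|---|---|
| 2% | 0.805 | 0.810 | 0.048 |
| 5% | 0.809 | 0.822 | 0.044 |
| 10% | 0.815 | 0.842 | 0.039 |

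The gain is 0.005 to 0.027. Omitting centre is slightly conservative and does not inflate error.

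**Step 5. Leaving the choice open.** Under the null, taking the better of the change t-test and ANCOVA at one visit gives type I error of 0.080 to 0.068 (s_b = 20, r 0.2 to 0.7) or 0.073 to 0.053 (s_b = 15). Counting success at either 1 or 2 years, each at 0.05, gives 0.091 to 0.078 for between-visit correlation 0.5 to 0.8.

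**The case against.** The strongest reply is that a method is implied. The power calculation concerns SNOT-22, states a null of equal means, and its 79 per arm matches a t-test, which is on the list. Under the postoperative-SD reading, the test it was sized for is a t-test on the postoperative score. Against that comparator ANCOVA at r = 0.2 gains only 0.818 − 0.803 = 0.015; the rest of the 0.21 is the penalty for analysing change when the correlation is low. That split is right, and the gain over the postoperative-score test instead grows with r (0.901 against 0.803 at r = 0.5). But the stated end point is the change, so the t-test on change is the fair comparator. A sample-size paragraph about a postoperative difference does not assign its analysis.

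It can also be said that adjustment is promised, that the long variable list serves other parts of the project and is never called the covariate list, and that *symptoms* or *other factors* could include baseline SNOT-22. All of that is fair. The plan does not forbid adjustment; it leaves the covariates and the model unnamed.

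Finally, choosing between the change t-test and ANCOVA means adding a method that is not listed. Choosing between the two listed tests gives a smaller inflation, to about 0.060 in a simulation with normal data. The open adjustment sentence still leaves the wider choice available.

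**Conclusion.** The concern holds, as something the sponsor should change and not as an invalid analysis. The primary end point has no named model, the listed tests that fit it are unadjusted, and the two obvious covariates are not named.

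The power gain over a t-test on change lies between about 0 and 0.21. Where it falls depends on the correlation, the baseline SD and the meaning of the SD of 20, none of which the documents settle. In every case examined ANCOVA kept at least 0.80 power, while the t-test on change could fall to 0.60; adjustment therefore protects the planned power against the ambiguity in the sample-size text. Almost all of the benefit comes from baseline SNOT-22 and little from centre. Confidence is medium because the size rests on assumed values.

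**What to change.** Name as the primary analysis a linear model of SNOT-22 adjusted for baseline SNOT-22 and centre, with all randomised patients in their allocated arm. A repeated-measures mixed model over all visits is preferable (arm, visit, arm by visit, baseline, baseline by visit, centre), with arm contrasts at 1 and 2 years, because it also uses the other visits of patients who miss one. A single-visit ANCOVA is simpler but does not do this. Keep the t-test and Mann-Whitney test as sensitivity analyses, and keep variables that arise after randomisation out of the primary model.

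State which time point is primary, or that both must succeed. Naming one costs no power. Requiring both lowers the unadjusted power from about 0.80 to between 0.70 and 0.74 (difference 9 at both, between-visit correlation 0.5 to 0.8, assumed).

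The cost is a paragraph of analysis-plan wording and slightly more analysis work. The named software can fit the model, and no patients, visits or data are added.

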This is a randomized controlled multicenter study that focuses on severe CRSwNP \pm asthma \pm AERD. Our primary objectives of this study are to find out:

- (1) Does extended surgery (total ethmoidectomy with opening of large sinuses) reduce HRQoL more effectively than partial ethmoidectomy? The primary end-point is the disease-specific questionnaire SNOT-22. The secondary objectives are to:
 - 1) Evaluate the outcome of surgery on polyp size, symptoms, general HRQoL, asthma specific HRQoL, olfaction, nasal patency, revision-rate, exacerbation-rate, lung function, costs and safety
 - 2) Develop the care pathway of CRS+/-asthma+/-AERD patients to improve outcomes and cost effectiveness of treatment
 - 3) Develop safe, specific and sensitive genome-based biomarkers for detection and management models for of severe airway inflammation and to further develop markers for progressive disease forms.
 - 4) To see if patients with certain genetic and/or clinical predispositions will benefit from extended surgery.

Significance: The clinical significance of this study is to develop cost-effective treatment models that will facilitate risk-estimation and prevention of the onset and the progression of severe CRSwNP, asthma and AERD. The potential societal impact is that it reduces the burden of inflammatory airway diseases. It will increase co-work between

clinicians, standardize treatment protocols and increase equality in health care in Finland. The academic impact is to train PhD students and clinicians. We will publish in peer reviewed international open access medical journals.

3. Methods

A. Operative study

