We aim at performing during the years 2-7 exome sequencing, mRNA sequencing and metatranscriptomics, immunohistochemistry, western-blot and ELISA in order to search for biological key-factors relevant for aggravated CRS and asthma and/or AERD.

For exome sequencing DNA is isolated from peripheral blood leucocytes, PCR enriched, and libraries are processed and sequenced on an Illumina HiSeq. For DNA methylation profiling, raw bisulphite treatment is performed on DNA. Oligonucleotide primers are synthesized. Libraries are processed and sequenced. SNPs and indels are called and annotation is performed by ANNOVAR. For metatranscriptomics RNA-Seq reads are trimmed and high-quality reads from each dataset are mapped to the non-redundant and truncated version of the ribosomal RNA SILVA reference. Reads are mapped to rRNA reference sequences and outputs are summarized for each phylotype. For transcriptomics total RNA from nasal cell brushings is extracted, enriched RNA-seq library is prepared and Nextera Primers are used. miRNA is PCR enriched and smallRNA libraries sequenced. Reads are corrected and aligned to the reference human genome (GRCh38/hg38). For metatranscriptomics RNA-Seq reads are trimmed and high-quality reads from each dataset are mapped to the non-redundant and truncated version of the ribosomal RNA SILVA reference. Reads are mapped to rRNA reference sequences and outputs are summarized for each phylotype. For quality control original cDNAs and RT-qPCR are used in the validation. cDNAs are amplified using TaqMan Universal PCR Master Mix. The expression levels are normalized with TBP or GAPDH. Small interfering RNAs targeting candidate genes are used. For exploring key-proteins we will perform immunohistochemistry, western-blot and ELISA to nasal specimens.

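### The only stated significance rule, p<0.05, is not lifted for the genome-scale omics analyses behind secondary objective 3, and no multiplicity control, layer-specific contrasts or independent replication are given

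*Combined protocol and SAP*

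**What the plan says.** The Statistics paragraph states one rule for significance: "P-values less than 0.05 are considered statistically significant". The sentence directly follows the one on Hardy–Weinberg and linkage-disequilibrium calculations and makes no exception. The same paragraph names, among the variables to be tested, "biological factors (predisposing SNPs, alterations in transcriptome or microbiome". It lists Fisher's exact, Chi-square, t and Mann–Whitney tests together with logistic and Cox models. The only adjustment it mentions is for covariates.

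Section 3.B is headed as a genome-scale search. Its samples "are taken from clinical trial participants and volunteer control subjects", and the sampling times are given thus: "These samples are collected in a time-series manner (pre-intervention, 24w post start of intervention". The programme is broad: "We aim at performing during the years 2-7 exome sequencing, mRNA sequencing and metatranscriptomics, immunohistochemistry, western-blot and ELISA". Methylation profiling and small-RNA sequencing are also described. The section covers laboratory work and read processing in detail but names no statistical test for the resulting data. On validation it says: "For quality control original cDNAs and RT-qPCR are used in the validation".

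This work serves secondary objective 3 in section 2: "Develop safe, specific and sensitive genome-based biomarkers".

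**The concern.** A threshold of 0.05 is meant for one test or a few. A genome-scale search tests many features, most of which may have no association with the phenotype. With no other rule in the plan, an analyst who follows the text literally would declare a marker at p<0.05 for each feature and each contrast, and chance findings could then outnumber real ones.

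The planned follow-up would not necessarily expose them. RT-qPCR on the original cDNAs repeats the measurement on the same material. It can show that an expression level was measured correctly, but not that its association with disease or outcome holds in other people. Small interfering RNA and protein work is planned too, but the plan does not say how its candidates are chosen and does not present it as replication.

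At stake is the specificity of the biomarkers that objective 3 seeks. The choice of contrasts and error control is also much less credible if it is made after results have been seen.

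**Working it through.** **Inputs.** From the document: threshold 0.05 (Statistics); 79 evaluable patients per arm (power calculation, section 3.A). Assumed, because the document does not give them: the number of features, the share truly associated, their effect sizes, independence between features, and groups of 79 v 79 for the omics. The numbers to be sequenced and of volunteer controls are not stated, so 79 v 79 is borrowed from the SNOT-22 calculation.

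**The plan's own figure.** A difference of 9, SD 20, two-sided alpha 0.05 and power 0.80 need 78.49 per arm by the t test, hence 79, with power 0.803. The 79 reproduces. It sizes SNOT-22 only; no figure of any kind is given for the omics.

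**Expected null hits per contrast**, for a test that holds its nominal size: features × 0.05.
- 100 features: 5
- 1,000 features: 50
- 20,000 features: 1,000

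**Share of hits that are false**, with true share π and power 0.8: 0.05(1−π) / [0.05(1−π) + 0.8π].
- π = 1%: 0.0495 / (0.0495 + 0.008) = 86%
- π = 5%: 0.0475 / (0.0475 + 0.040) = 54%
- π = 10%: 0.045 / (0.045 + 0.080) = 36%

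**Sparse variants.** Size at 0.05, conditional on the total number of carriers, 79 v 79, two-sided:

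| Carriers | Fisher's exact | Chi-square, uncorrected |
|---|---|---|
| 5 | 0 (smallest p 0.0586) | 5.9% |
| 8 | 0.65% | 6.3% |
| 10 | 1.8% | 9.8% |

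The case of 10 carriers shows why the tests differ. A 2:8 split gives Chi-square = 158 × (2×71 − 77×8)² / (79 × 79 × 10 × 148) = 3.843, just above the critical value 3.841, so it counts as significant. Fisher's test needs a 1:9 split or a more extreme one. At 20 and 40 carriers Fisher's size is 2.9% and 4.3%. So 5% is a guide and not a bound: the true rate depends on which listed test is used.

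**What false-discovery control would change.** Simulation of 1,000 independent continuous features, two-sample t tests, 79 v 79, 2,000 runs. An effect of 0.449 SD has 80% power at 0.05. Entries are mean false / true hits:

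| Scenario | p<0.05 | Benjamini–Hochberg 5% |
|---|---|---|
| 10 true, 0.449 SD | 49.4 / 8.0 | 0.14 / 1.4 |
| 10 true, 0.9 SD | 49.6 / 10.0 | 0.55 / 9.8 |
| 100 true, 0.449 SD | 45.1 / 79.9 | 1.8 / 37.7 |

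False-discovery control removes nearly all the chance hits. It costs most of the true ones when effects are modest and rare, and almost none when they are large.

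**The case against.** The strongest reply is that silence is not a decision. The plan never says that 0.05 will be applied to each feature, and it does not rule out a later correction. The tests listed are general clinical ones, and SNPs appear beside age, gender and occupation, which can be read as a few known candidates entered in models. The background section mentions about 100 associated SNPs. This stands in part: feature-by-feature use is an inference, and the consequences are conditional on it. But the plan does not limit testing to known SNPs, the transcriptome and microbiome layers are not framed as candidate lists, and even 100 features would give about 5 null hits per contrast.

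A reader might infer that the plan names no contrasts at all. It does not go that far. The Statistics paragraph names the two operations, and ASA versus placebo desensitization. Section 3.B implies participants versus volunteers, before versus 24 weeks, and asthma or AERD status. What is missing is their assignment to the omics layers.

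A reader might also take 5% as the most that could go wrong. The Chi-square figures above show otherwise for sparse variants.

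It can also be said that this is discovery work, where losing true markers matters more than carrying false ones. The choice of false-discovery level is indeed a judgement. But the document does not label the omics work exploratory, and objective 3 asks for specific markers.

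**Conclusion.** The concern holds as a gap in the rules for secondary objective 3. One unqualified 0.05 rule sits in the paragraph that also covers the omics variables, and nothing in the document adds multiplicity control, layer-specific contrasts or independent replication. If the rule is followed feature by feature, expect about 50 chance hits per 1,000 null features per contrast, fewer or more for sparse variants according to the test. With 1% to 10% of features truly associated at 80% power, roughly 86% to 36% of the hits would be false. Feature counts, true shares, effect sizes, independence and 79 v 79 are all assumptions.

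Two wider readings are not supported. The primary SNOT-22 comparison is not affected, because this point concerns only the omics analyses. Objective 4, on whether predisposed patients benefit from extended surgery, raises a separate question, since no arm-by-factor interaction is specified. That question may be taken up on its own but adds no weight here.

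This should be corrected before the omics data are analysed. It does not threaten the trial's main result.

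**What to change.** In the Statistics section:
- State that the unadjusted 0.05 rule does not apply to the omics analyses.
- Name the contrasts for each layer before analysis. Arm and time point, for instance, do not apply to inherited exome variants.
- Control the false discovery rate within each layer-by-contrast family, for example by Benjamini–Hochberg at 5%, and report how many families there were and how many features were tested in each.
- Call a marker a candidate unless it has been replicated in independent subjects.

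The rule for the primary and clinical secondary endpoints stays as it is.

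The cost is a few sentences and routine computation, with no extra patients or samples. A replication cohort is not required by this change; without one, markers simply remain candidates. The real price is sensitivity: in the 1,000-feature example about 1.4 instead of 8.0 of 10 true markers survive at modest effect, and 9.8 instead of 10.0 at 0.9 SD. Control within families also sets no bound on the error rate across all families together, which is why their number should be reported.
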